1. To evaluate whether immunization with a DNA vaccine encoding prostatic acid phosphatase (PAP, pTVG-HP) can augment PAP-specific effector and memory T cells following treatment with sipuleucel-T.

[figure not shown]
Secondary Objectives:

1. To determine 12-month radiographic progression-free survival
2. To determine median time-to-radiographic progression as a function of baseline time point (pretreatment or 3-months post treatment)
3. To evaluate effects of treatment on changes in serum PSA level and changes in PSA doubling time

Laboratory and Exploratory Objectives:

1. To determine overall survival
2. To evaluate effects of treatment on number of circulating tumor cells as determined by PSA ELISPOT
3. To evaluate PAP-specific antibody and T-cell immune responses following treatment with sipuleucel-T and DNA vaccine
4. To determine whether PAP-specific immune response is associated with prolonged (1 year) radiographic progression-free survival
5. To determine whether baseline immune responses (Th1 type or regulatory type) predict for immune responses elicited/augmented following treatment with sipuleucel-T +/- DNA vaccine
6. To determine whether treatment elicits immunologic antigen spread to other prostate associated antigens

Study Scheme:

Study Calendar:

Vaccine / Treatment Visit:	Pre-Screen (within 4 weeks of Screen)	Screen/Randomization (within 2 weeks of day 1)	Day 1 – sipuleucel-T collection #1	Day 4 – sipuleucel-T infusion #1	Day 15 – sipuleucel-T collection #2	Day 18 – sipuleucel-T infusion #2	Day 29 – sipuleucel-T collection #3	Day 32 – sipuleucel-T infusion #3	Day 43 – sipuleucel-T follow-up / DNA imm #1 ^a	Day 57 – DNA imm #2 ^a	Day 71 – DNA imm #3 ^a	3-Month Followup (Day 85) – DNA imm #4 ^a	6-Month Follow up (Week 24) – DNA imm #5 ^a	9-Month Follow-up (Week 36) – DNA imm #6 ^a	12-Month (Week 48) Follow-up and/or End of study visit
History & Physical Exam															
History	X														
Consent	X														
Physical Exam, ECOG PS		X			X		X		X			X	X	X	X
Vital signs		X		X	X	X	X	X							
Toxicity assessment ^b		X			X		X		X			X	X	X	X
Injection site inspection									X	X	X	X	X	X	X
Lab Tests															
CBC with differential and platelets ^c		X			X		X		X			X	X	X	X
Creatinine, alk phos, SGOT, total bilirubin, amylase, LDH		X							X			X	X	X	X
Serology for HIV Ab/Ag combo, Hepatitis B Surface Ag, Hepatitis C AB		X													
Serum testosterone, ALT		X													
PSA ^d and PAP		X							X			X	X	X	X
Procedures															

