CT abdomen/pelvis ^e	X											X ^f	X	X	X ^g
Bone scan ^e	X											X ^f	X	X	X ^g
Leukapheresis		X ^h	X		X		X						X ^{h,i}		
Sipuleucel-T infusion				X		X		X							
Tetanus immunization		X													
DNA immunization – ARM 2 PATIENTS ONLY ^a									X	X	X	X	X	X	
Blood for CTC analysis		X							X			X	X	X	X
Blood for immune studies ^j		X							X			X	X	X	X ^k

Note: Grey regions indicate those tests or procedures or visits only applicable to subjects treated on Arm 2. Acceptable delays in study treatments or procedures may result in corresponding delays of subsequent visits. Annual long term follow up will occur for up to five years. See Section 9 for more details.

^a ARM 2 Only: Biweekly DNA immunization (#1-3) can be +/- 3 days; quarterly DNA immunization (#4-6) can be +/- 7 days from expected date determined from prior visit.

^b Study coordinator or research nurse review of systems, including ECOG PS

^c CBC with differential and platelets to be performed within 72 hours prior to leukapheresis (for Sipuleucel-T treatment) unless an event occurs that would require it be drawn sooner for safety considerations, or if required sooner per institutional requirements or MD discretion. A CBC result within 7 days prior to leukapheresis for research is ideal.

^d PSA measurements must be performed at the 3-month intervals defined, but can be more frequent if clinically indicated.

^e Radiographic studies (CT scans and bone scans) can be performed +/- 7 days of the study visit

^f Staging studies (CT and bone scan): scan progression between Screening and Month 3 will not be used to define radiographic progression for the purposes of this study and will not necessitate subjects to come off study. Patients should come off study at this time point only due to symptomatic progression requiring other treatment for prostate cancer.

^g Radiographic studies not required at off-study time point if subject already met time-to-progression endpoint and/or studies already performed within 1 month; scans otherwise performed every 12 weeks

^h Leukapheresis collected (+/- 7 days) for research, not preparation of sipuleucel-T product

ⁱ If leukapheresis is not able to be obtained at Month 6 visit, then up to 150 ml may be obtained via peripheral blood draw as an alternative.

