Evidence that the toxicity rate is excessive will be considered sufficient if the lower limits of the 90% one-sided confidence intervals for the estimates of the true toxicity rates exceed the toxicity limits defined above (i.e., 20% for Grade 3 events and 10% for Grade 4 events), after the first 5 patients have been accrued. Operationally, this will occur if any of the following events occurs within a study arm: Grade ≥ 3 events (or Grade >1 autoimmune events) are present in at least 3 out of 5, 4 out of 9 (or less), 5 out of 13 (or less), or 6 out of 15 (or less) of the subjects accrued (within a study arm). Furthermore, accrual will be temporarily suspended if any of the following events occur: Grade 4 events are present in at least 2 out of 5, 3 out of 11 (or less), or 4 out of 15 (or less) of the subjects accrued (within a study arm).

If one of these thresholds is reached, accrual will be temporarily suspended and the study will be reviewed by the UW DSMC (data and safety monitoring committee) to consider safety and dose modifications with respect to treatment arm. Once the study is suspended, it would only be reopened if modifications could be made, and approved by the DSMC and the UW-IRB, to assure that patient safety is reestablished. If not, the study would be closed.

B. Endpoints

Patients will come off study at the time of radiographic disease progression, with progression being defined only AFTER the first 3-month staging evaluation, at the time of undue toxicity (as defined below), or at the discretion of the patient and treating physician that other therapies for prostate cancer are warranted. Patients should be discouraged from discontinuing protocol treatment for PSA rise only. Patients will continue to have blood drawn for immune studies, as per study calendar, up to one year after screening, even if off study prior to that time. The 6 month visit, in particular, is important to collect for the purpose of endpoint analysis. Subjects who have not come off study earlier for these reasons will come off study at the end of the one-year treatment period.

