To assess objective response, it is necessary to estimate the overall tumor burden at baseline (for purposes of comparison, “baseline” imaging will be that obtained at 3-month time point) to which subsequent measurements will be compared. Measurable disease is defined by the presence of at least one measurable lesion.

All measurements should be recorded in metric notation by use of a ruler or calipers. The same method of assessment and the same technique should be used to characterize each identified lesion at baseline and during follow-up. All pre-treatment evaluations should be performed as closely as possible to the beginning of treatment and not more than four weeks before registration.

The term evaluable in reference to measurability will not be used because it does not provide additional meaning or accuracy.

At baseline, tumor lesions will be characterized as either measurable or non-measurable.

NOTE: While progression will be documented from pre-treatment staging studies in all individuals, the intent of these measurements in this trial will be to determine whether “baseline” evaluation for immune-based treatments is preferable at a later time point after the therapy has been given the opportunity to exert an anti-tumor effect. Hence, the “baseline” evaluation for determining progression will be the staging studies performed at day 85 (3 months). Objective progression at Month 3 from the pre-treatment scans will not be used to alter treatment unless the

patient has symptomatic disease requiring other therapy and thereby needs to discontinue treatment.

1. Measurable

Lesions that can be accurately measured in at least one dimension (longest diameter to be recorded) as ≥ 20 mm (2.0 cm) with conventional techniques or as > 10 mm (1.0 cm) with **spiral** CT scan. For a lymph node to be considered pathologically enlarged and measurable, it must be ≥ 15 mm in short axis when assessed by spiral CT.

If the measurable disease is restricted to a solitary lesion, its neoplastic nature should be confirmed by cytology/histology.

Tumor lesions that are situated in a previously irradiated area are not considered measurable.

2. Non-Measurable

All other lesions, including small lesions [longest diameter < 20 mm (2.0 cm) with conventional techniques or < 10 mm (1.0 cm) with **spiral** CT scan], lymph nodes < 15 mm in short axis, and truly non-measurable lesions.

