An immune response will be defined based on the detection of augmented numbers of PAP-specific effector (IFN γ -secreting and/or granzyme B-secreting) and/or memory (proliferating) T-cell immune response after immunization, using blood obtained at 6 months for the primary analysis compared with pre-treatment. Specifically, a positive antigen-specific response resulting from immunization will be defined as a PAP-specific response by two or more of these three tests detectable at the 6-month post-treatment time point that is significantly ($p < 0.05$, two-sided using a two-sample t-test) higher than to media only, at least 3-fold higher than the mean baseline value, and with a frequency > 10 per 10^6 PBMC, based on 8-well replicate assays (for ELISPOT-based assays) or triplicate assays (for proliferation analysis). Otherwise, a patient will be declared as an immune non-responder.

Immune response will be determined as a static time point at 6 months, and “durable” immune responses will also be determined by the presence of a PAP-specific immune response by the criteria above detectable at 3, 9, or 12 months after study entry.

C.2. Secondary Clinical and Immunological Endpoints

C.2.1. Time to Progression

Time to progression will be defined as a function of baseline time points in two ways:

- (1) *Time to progression from randomization*: Time elapsed from randomization until disease progression or death. If a patient doesn't experience a disease progression or death event before the end of the follow-up period, then the observation for this patient will be censored.
- (2) *Time to progression from 3 months post-randomization*: Time elapsed from the 3 months disease progression assessment until disease progression or death. If a patient doesn't experience a disease progression or death event before the end of the follow-up period, then the observation for this patient will be censored.

The rationale for defining time to progression as a function of baseline time points (date of randomization and 3-month disease assessment) is described in Section 6 (B).

C.2.2. Twelve-month Progression Free Survival Rate

The 12-month progression free survival rate will be defined as the proportion of patients progression free at the 12 month (post-randomization) disease assessment time point.

C.2.3. Overall Survival

Overall survival will be defined as the time interval from randomization to death from any cause or to the last follow-up in censored patients.

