The 12-month progression-free survival rate will be estimated for each arm using the Kaplan-Meier method. The 12-month progression-free survival rate, along with the corresponding two-sided 95% confidence intervals, will be reported for each arm. In order to evaluate the 12-month progression-free rate as a function of baseline time point (pretreatment or 3-months post treatment), the analysis will be conducted using two different baseline values: (1) Date of randomization, and (2) 3-months disease assessment.

G.4.2. Analysis of Progression-Free Survival

Progression-free survival will be estimated for each arm using the Kaplan-Meier method. The median progression-free survival, along with the corresponding two-sided 95% confidence intervals, will be reported for each arm. The comparison of progression-free survival between study arms will be performed using the stratified (by estimated survival at baseline, < 18 months vs. \geq 18 months) log-rank test. In order to evaluate progression-free rate as a function of baseline time point (pretreatment or 3-months post treatment, the analysis will be conducted using two different baseline values: (1) Date of randomization, and (2) 3-months disease assessment.

G.4.3. Analysis of Overall Survival

Overall survival will be estimated for each arm using the Kaplan-Meier method. The median overall survival, along with the corresponding two-sided 95% confidence intervals, will be reported for each arm. The comparison of overall survival between study arms will be performed using the stratified log-rank test.

G.4.4. Analysis of Changes in PSA Values, PSA Kinetics and PSA Doubling Time

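### Section 12.G.4.1 plans a 12-month progression-free rate from the month-3 assessment that the imaging schedule cannot deliver, and gives the randomization-based rate no censoring date or reading time

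*Combined protocol and SAP*

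**What the plan says.** Section 12.G.4.1 estimates the 12-month rate in each arm by Kaplan-Meier with a 95% confidence interval, from two time origins: "In order to evaluate the 12-month progression-free rate as a function of baseline time point (pretreatment or 3-months post treatment". Section 12.C.2.1 defines the second clock as "Time elapsed from the 3 months disease progression assessment until disease progression or death". Section 7.A fixes that baseline: the "evaluation for determining progression will be the staging studies performed at day 85 (3 months").

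Section 12.C.2.2 defines the 12-month rate itself as "the proportion of patients progression free at the 12 month (post-randomization) disease assessment time point".

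The last column of the Study Calendar is headed "12-Month (Week 48) Follow-up and/or End of study visit". Section 9.O gives that visit a window of 7 days either way, and Study Calendar footnote e adds "Radiographic studies (CT scans and bone scans) can be performed +/- 7 days of the study visit". Section 6.B ends participation there: "Subjects who have not come off study earlier for these reasons will come off study at the end of the one-year treatment period". Section 9.P then provides an annual telephone contact, counted from registration, which collects stage, treatments, PSA and date of death. It lists no scans.

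On censoring, 12.C.2.1 says only that a patient with no event by the end of follow-up is censored. It does not say at which date.

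**The concern.** A Kaplan-Meier rate at 12 months needs patients who are still being assessed at 12 months. From the month-3 baseline, that means imaging at about study month 15, and the schedule has none. The curve would be undefined at that point, or zero if the last observation happened to be an event. The likely repair at analysis time is to read it at study month 12 and keep the label, which would present a shorter-term rate as a 12-month one.

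From randomization the problem is different. The last scans are spread over several weeks, and the plan does not say when a progression-free patient is censored or at which day the curve is read. With 15 patients per arm, those unstated choices can move the estimate by more than 10 percentage points. The rate concerned is secondary objective 1.

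**Working it through.** The plan states no progression-free rate, event count or precision, so there is no figure of its own to reproduce. One month is taken as 365.25/12 = 30.44 days.

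**1. Follow-up from the month-3 assessment**

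- Day 85 is 84 days after day 1, and week 48 is 336 days after day 1 (Study Calendar, 9.L, 9.O).
- Nominal: 336 - 84 = 252 days; 252 / 30.44 = 8.3 months.
- Every window used (visit 7 days plus scan 7 days, at both ends): (336 + 14) - (84 - 14) = 280 days; 280 / 30.44 = 9.2 months.
- Needed: 365 days. The shortfall is 113 days nominally and at least 85 days.
- Permitted sipuleucel-T delays do not help. Section 9 moves the whole calendar, so the month-3 scan moves as well.

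**2. Last scan counted from randomization**

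- Randomization is part of screening, 0 to 14 days before day 1 (9.B).
- Nominal latest: 336 + 14 = 350 days (11.5 months).
- With visit and scan windows: 350 + 14 = 364 days.
- With two infusion intervals each lengthened from 14 to 21 days (9, introduction): 364 + 14 = 378 days.

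**3. Effect of the censoring date: an example**

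Assumed, not from the plan: 15 patients in an arm (the planned number, 12.F); 9 progress before week 48; 6 are scanned at week 48 on distinct days; 2 of those 6 have progressed; the 4 others are censored at that scan.

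- Observed proportion free: 4/15 = 26.7%.
- Kaplan-Meier before the last round: 6/15 = 0.40.
- An event with k patients at risk multiplies the curve by (k - 1)/k. For k = 1 to 6 the factors are 0, 0.500, 0.667, 0.750, 0.800 and 0.833.
- The two events can fall in 15 equally likely pairs of positions. The factors sum to 3.55 and their squares to 2.591, so the pair products sum to (3.55² - 2.591)/2 = 5.006.
- Mean: 0.40 × 5.006/15 = 0.133, or 13.3%.
- Highest, both events first: 0.40 × (5/6) × (4/5) = 26.7%. Lowest, the last-scanned patient progresses: 0%, in 5 of 15 orderings.
- All six at one nominal time, events before censorings: 0.40 × (1 - 2/6) = 26.7%, equal to the proportion.

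**4. Effect of the censoring date: simulation**

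Assumed: 15 patients; 2,000 runs; scans at weeks 12, 24, 36 and 48 with uniform scatter of 7 days either way; randomization 0 to 14 days before day 1; exponential progression after month 3; no deaths or dropout; censoring at each patient's last scan; curve carried forward to day 365.

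| Assumed median after month 3 (months) | Kaplan-Meier at day 365 | Proportion free at week-48 scan | True rate at day 365 | Runs with Kaplan-Meier = 0 |
|---|---|---|---|---|
| 4 | 0.129 | 0.237 | 0.210 | 38% |
| 6 | 0.243 | 0.386 | 0.354 | 25% |
| 9 | 0.365 | 0.533 | 0.500 | 19% |
| 12 | 0.470 | 0.620 | 0.595 | 14% |
| 18 | 0.593 | 0.728 | 0.707 | 10% |

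Including runs with 14 days of scatter, Kaplan-Meier lies 11 to 17 points below the observed proportion and 8 to 15 points below the true rate. Other conventions give other answers:

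- All scans at one nominal time: Kaplan-Meier equals the proportion (for example 0.385 and 0.385 at a median of 6 months).
- Progression-free patients censored after day 365: 2 to 3 points above the true day-365 rate.
- Curve read at day 336 from randomization: too high (0.511 against an observed 0.386 at a median of 6 months), because many last scans have not yet happened.

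**The case against.** For the month-3 origin, the best defence is that 12.C.2.2 ties the 12-month rate to randomization, so the second analysis could mean status at study month 12 measured against the month-3 scan. That quantity can be estimated. It is still an 8-9-month rate on the clock that 12.C.2.1 defines, so the label needs correcting. Imaging can also occur outside the schedule: 6.B allows scans when clinically indicated, and 7.B.2 asks for a repeat bone scan at least 6 weeks later in some cases. Six weeks added to the longest follow-up gives 280 + 42 = 322 days, still short of 365, and such scans arise from clinical need or suspected progression, not for every progression-free patient.

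For the randomization origin, much of the objection stands. A reader might infer that the planned estimate is necessarily biased low. The documents do not support that, because they never say that patients are censored at their own last scan. Section 12.F promises at least 12 months of follow-up, and nominal times or later censoring remove the low bias. Nor is every last scan before day 365, since permitted delays can carry it to day 378. Defining a proportion and estimating it by Kaplan-Meier is not a contradiction in itself: the two agree when nobody is censored before the landmark.

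A reader might also infer that part of secondary objective 2 is lost. It is not: that objective concerns the median, which is analysed in 12.G.4.2.

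**Conclusion.** The month-3-origin 12-month rate cannot be estimated from the schedule. It falls short by 113 days nominally and by at least 85 days. This rests on the visit calendar and its windows alone, and on 12 months meaning 12 months from the clock in 12.C.2.1.

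The randomization-origin rate is under-specified, not shown to be wrong. If progression-free patients are censored at scattered last-scan dates and the curve is read at day 365, the low bias is substantial. Its size depends on the assumed event counts, scan scatter and progression medians above; its absence under nominal times does not.

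This should be fixed before analysis. It affects secondary objective 1 in a 30-patient pilot whose primary endpoint is immunological, and 12.G.4.1 asks for estimates and intervals without a between-arm test.

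**What to change.** - **Month-3 origin (12.G.4.1):** replace the 12-month rate with the rate at the week-48 scan, labelled as 36 weeks after the month-3 assessment.
- **Randomization origin (12.C.2.2 and 12.G.4.1):** choose one of two estimators and state it. Either use the proportion progression-free at the week-48 assessment, as 12.C.2.2 already defines it; or use Kaplan-Meier on nominal scan times (weeks 12, 24, 36 and 48), read at week 48, with events counted before censorings at that time. The proportion also needs a stated rule for patients who leave without progression before week 48. Kaplan-Meier on nominal times handles them as censored.

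The change needs no new visits, scans or patients. The only cost is that the second rate carries a shorter, accurate label.

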200,000 cells/well of a 96-well plate, and all spots will be counted (i.e. screening for events among $\sim 20 \times 10^6$ total PBMC). Multiple replicates to determine standard deviation are not feasible. Other methods of CTC enumeration, such as by flow cytometry, may also be used.

C. Serum PSA Doubling Time Response

See Section 12 for further details. Serum PSA doubling-time response will be considered a secondary endpoint. The pre-treatment serum PSA doubling time will be calculated from all serum PSA values available for the three-month period prior to study treatment, not on other treatments for prostate cancer, up to and including the PSA value obtained at screening, using the Memorial Sloan-Kettering Cancer Center nomogram (<http://www.mskcc.org/applications/nomograms/prostate/PsaDoublingTime.aspx>). The post-treatment serum PSA doubling time will be calculated using the same algorithm and using all serum PSA values available during the time patients are on study beginning with the PSA value obtained at day 1.

REPORTING AND RESPONSE DEFINITION: PSA doubling times for the pre-treatment and post-treatment periods will be defined as above. An increase in the PSA doubling time to at least double the baseline value will be defined as a PSA doubling time “response” [64].

11. Reporting Adverse Events

Please see section 14 below, which contains in detail the policy and procedures for patient safety monitoring and adverse event reporting.

A. Definition

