PSA values will be summarized using standard descriptive statistics for each defined assessment time point (baseline, 3, 6, 9, and 12 months) in terms of number of observations, means, standard deviations, medians and ranges, stratified by study arm. Percentage changes from baseline to the 3, 6, 9, and 12 months assessment will be calculated. Changes within each arm will be evaluated using a paired t-test or nonparametric Wilcoxon Signed Rank test, if the percentage changes are not normally distributed. Analysis of variance, which will include study arm and baseline predicted survival (< 18 months vs. \geq 18 months) will be used to compare percentage changes in PSA values between study arms. If the percentage changes are not normally distributed and if a normality-improving data transformation is unavailable, then the stratified, nonparametric Wilcoxon rank-sum tests will replace the planned ANOVA. Changes in PSA levels will be presented graphically using waterfall plots.

PSA response rates (CR / PR) will be summarized in tabular format and compared between study arms using the Cochran-Mantel-Haenszel test, stratified by baseline estimated survival (< 18 months vs. \geq 18 months).

PSA doubling time for each patient is estimated as: $PSADT = \log(2)/b$, where b is the OLS estimator of slope parameter of the linear regression model $\log(PSA) = \alpha + \beta * \text{month} + \epsilon$. This method may result in negative PSA doubling time estimates. For analysis purposes, negative PSA doubling time estimates will be replaced by fixed positive PSA doubling time values (e.g., by the largest observed positive PSA doubling time value). Serum PSA doubling time will be summarized for each study arm by standard descriptive statistics in terms of means, standard deviations, medians and ranges. Percentage changes between pre-treatment and post-treatment PSA doubling times will be computed. Changes between pre- and post-treatment serum PSA doubling time within each arm will be assessed using a paired t-test and/or non-parametric Wilcoxon Signed Rank test. A two-sample t-test or non-parametric Wilcoxon Rank Sum test will be used to compare the changes in PSA doubling time from the pre- to the post-treatment assessments between study arms.

G.5. Correlative Analyses

G.5.1. Analysis for evaluating effects of treatment on the number of circulating tumor cells as determined by PSA ELISPOT

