The number of circulating tumor cells per million PBMC will be summarized in terms of medians and ranges, stratified by study arm and assessment time point. The nonparametric Wilcoxon Signed Rank test will be used to evaluate the effects of treatment on the number of circulating tumor cells within each study arm. The comparison of changes in the number of circulating tumor cells between study arms will be performed using the nonparametric, stratified, Wilcoxon Rank Sum test. Results will be presented graphically over time, and trends (increase, decrease, stable) will be assessed over time.

G.5.2. Analysis for evaluating PAP-specific antibody and T-cell immune responses following treatment with sipuleucel-T and DNA vaccine

PAP-specific antibody and T-cell immune responses, evaluated by multiple different measures described in Section 10.A, following treatment with sipuleucel-T and DNA vaccine will be summarized in tabular format.

G.5.3. Analysis for evaluating whether PAP-specific immune response is associated with prolonged (1 year) progression-free survival

Logistic regression analysis will be conducted to evaluate whether PAP-specific immune response is associated with prolonged (1-year) progression-free survival. The dependent variables will be 12-month progression free survival while treatment arm and PAP-specific immune responses (no vs. yes) will be included as covariates. The results will be reported in terms of odds ratios and the corresponding 95% confidence intervals.

G.5.4. Analysis for evaluating whether baseline immune responses (Th1 type or regulatory type) predict for immune responses elicited/augmented following treatment with sipuleucel-T +/- DNA vaccine

Logistic regression analysis will be conducted to evaluate whether baseline immune responses (Th1-type or regulatory type) predict for immune responses elicited/augmented following treatment with sipuleucel-T +/- DNA vaccine. 6-month and durable immune response at 3,6 or 12 months will be included as dependent variables in this analysis while treatment arm and baseline PAP-specific immune responses (no vs. yes) will be included as covariates. Odds ratios and the corresponding 95% confidence intervals will be reported.

G.5.5. Analysis for evaluating whether treatment elicits immunologic antigen spread to other prostate associated antigens

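### The month-9 and month-12 PSA-change tests use only patients who have not yet progressed; PSA level should be compared with a longitudinal model

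*Combined protocol and SAP*

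**What the plan says.** Change in serum PSA level is part of secondary objective 3. Section 12.G.4.4 summarises PSA at baseline and at months 3, 6, 9 and 12: "Percentage changes from baseline to the 3, 6, 9, and 12 months assessment will be calculated". Changes within each arm get a paired t-test or signed-rank test. The comparison between arms is "Analysis of variance, which will include study arm and baseline predicted survival", with a stratified rank-sum test as fallback. No model links the visits, and nothing is said about patients without a value at a visit. Section 12.G.1 sets two-sided 0.05 for these comparisons, without adjustment.

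Section 6.B sets the exit rule: "Patients will come off study at the time of radiographic disease progression, with progression being defined only AFTER the first 3-month staging evaluation". It then says what goes on afterwards: "Patients will continue to have blood drawn for immune studies, as per study calendar, up to one year after screening, even if off study". PSA is not named there. Section 10.C limits the post-treatment doubling time to on-study data, "using all serum PSA values available during the time patients are on study beginning with the PSA value obtained at day 1". After exit, Section 9.P asks only for a recent PSA value at the annual contact.

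In Section 9.M, the month-6 PSA and the month-6 scans belong to the same visit. Section 9.O includes a PSA draw at the off-study visit.

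**The concern.** A patient whose disease progresses on the month-6 scan has no scheduled PSA at months 9 or 12. One who progresses at month 9 has none at month 12. Progression is plausibly tied to PSA growth, so the late tests are run in a group chosen after randomisation by an outcome related to the one being tested.

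Three things follow:
- The late rise in PSA within an arm is understated.
- The contrast between arms can be diluted, or shifted if the arms progress at different rates. An arm that progresses later keeps its faster PSA risers longer.
- Power falls as patients leave, although their earlier PSA values are on file.

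Section 2.E says the trial may supply clinical endpoints for later studies, so a distorted late PSA contrast could mislead that use.

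**Working it through.** **1. Who has a PSA value at each visit.** Progression seen at month 3 removes nobody unless symptoms require other treatment. The first scheduled scan that can remove a patient is month 6, and PSA is taken at that visit, so month 6 loses only earlier exits (symptoms, toxicity, patient or physician choice, unscheduled scans). Months 9 and 12 hold only patients not progressed at an earlier scan.

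**2. Figures in the plan.** No power, effect size, SD or retention is given for PSA. Table 12.2 covers the immune response rate only, so there is no plan figure to reproduce.

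**3. Numbers left per arm (assumed exit rates).** Start from 15.
- 30% exit per scan: month 9, 15 × 0.70 = 10.5; month 12, 15 × 0.70² = 7.4.
- Exponential progression after month 3 with median 14.6 weeks: month 9, 15 × 0.5^(12/14.6) = 8.5; month 12, 15 × 0.5^(24/14.6) = 4.8. The 14.6 weeks is a time to progression quoted in Section 2.B from a pre-treatment baseline, so it is only a guide.
- Medians of 11.7 to 36 weeks: 7.4 to 11.9 at month 9 and 3.6 to 9.4 at month 12.

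**4. Power lost through numbers alone.** A standardised difference d = 1.06 has 80% power with 15 per arm (two-sided t-test, 0.05). The noncentrality is d√(n/2).
- n = 15: 1.06 × √7.5 = 2.90, power 80%.
- n = 8.5: 1.06 × √4.25 = 2.19, power 53%.
- n = 4.8: 1.06 × √2.4 = 1.64, power 30%.
- Medians of 11.7 to 36 weeks: 47–70% at month 9 and 22–58% at month 12.

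**5. Power with selection (simulation).** Model: log PSA = patient intercept + patient slope × month + error. All inputs are assumed. Visit-wise tests are t-tests on log change, a simplification of the planned ANOVA on percentage change. The mixed model has one straight slope per patient, with variances treated as known.

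| | Set A | Set B |
|---|---|---|
| Mean slope (SD) per month | 0.12 (0.08) | 0.12 (0.10) |
| Residual SD | 0.2 | 0.2 |
| Slope difference | 0.08 | 0.10 |
| Exit | 30–35% per scan | median 14.6 weeks after month 3 |
| Hazard multiplier per SD of slope | e^0.5 to e^0.7 | e^0.7 |
| Power, month 6 | 62–63% | 67% |
| Power, month 9 | not run | 41% |
| Power, month 12 | 32–40% | 26% |
| Power, mixed model | about 70% | 73% |

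**6. Bias.**
- Within arm: the true mean 12-month log rise is 0.12 × 12 = 1.44 (e^1.44 = 4.2-fold). Patients remaining at month 12 show about 0.9 to 1.1 in set A (2.5- to 3.0-fold). In set B, Arm 1 shows 0.70 against 1.43 for all.
- Between arms with a real PSA effect (set B): −1.19 shrinks to −0.90, a loss of 0.29/1.19 = 24%.
- Between arms with no PSA effect but a 40% lower progression hazard in Arm 2: about +0.10 to +0.15 in set A (against the vaccine), with a standard error of 0.45–0.49, so about 0.3 standard errors. Rejection is 5–7%, and the mixed model is biased by about 0. Set B gives +0.21, with rejection about 6%.
- With no effect on either outcome, rejection stays near 5%.

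**7. The planned doubling-time comparison.** Under set A, the rank-sum test on change in doubling time, including the replacement of negative estimates, had 74–75% power. This takes the pre-treatment slope to be the patient's own untreated slope.

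**The case against.** The strongest reply is that the plan already holds a slope analysis. Doubling time is fitted per patient from all on-study values, so early leavers contribute, and under the same assumptions it does at least as well as the mixed model. This stands. A reader might infer that the PSA evaluation as a whole loses much of its power; it does not. The weakness is confined to PSA level.

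Three other inferences are tempting but unsupported:
- **Month 6 is already selected.** The scan that can first remove a patient and the month-6 PSA fall at one visit, so that comparison is largely complete.
- **Circulating tumor cells have the same problem.** The documents do not show that these draws stop. Section 10.B ties them to the immune time points, which continue after exit, and Appendix B puts them in one row with the T-cell blood. The calendar row for them lacks the off-study footnote, so the matter is unsettled, but it leans towards continued collection.
- **The late tests give many false positives.** Rejection stays at about 5–7% even when progression differs between arms.

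It is also fair to say that every PSA input above is assumed, that these are unpowered secondary tests in a 30-patient pilot, and that change while on study is a legitimate description. Finally, one straight slope from screening sits badly with the delayed effect that the protocol expects. That argues for a more flexible model, not for the visit-wise tests.

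**Conclusion.** The point holds for the PSA-level tests at months 9 and 12, within and between arms. That selection exists follows from the exit rule and the PSA schedule. Its size does not, because progression after month 3, PSA variance and the link between PSA growth and progression are all assumed.

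Under set A, month-12 power is about 40% or a little less, against about 70% for a straight-slope mixed model. The bias when only progression is delayed is about +0.1 log units (e^0.1 = 1.11, so about 11% in PSA). That is small against the noise of one trial. The understated rise within each arm is larger. The more flexible models proposed below will have somewhat less power than 70% if the true effect is a constant slope difference. The primary endpoint and the doubling-time comparison are not touched. This is an inexpensive improvement to a secondary analysis, not a threat to the trial.

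**What to change.** In Section 12.G.4.4, make the between-arm test of PSA level a linear mixed model on log(PSA):
- Use all on-study values (screening, day 43, months 3, 6, 9 and 12) and the off-study draw at its actual date.
- Include predicted-survival stratum, time, and arm by time. Take time either as visit category or as a slope that may change after vaccination starts at day 43. State in advance which form is primary, how the off-study draw is assigned if visits are categories, and which contrast is tested.
- Use a patient-level random intercept and slope, with a small-sample correction for the degrees of freedom.
- Keep the month-9 and month-12 percentage-change tables as descriptive, with the number remaining in each arm.

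No change is asked for month 6 as a time point, for doubling time, or for circulating tumor cells.

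The cost is SAP wording; no visit or sample is added. Section 12.G.3 already specifies a mixed model for repeated immune responses, so the approach is in keeping with the plan. The downside should be written down: the model assumes that exit depends on PSA already observed, and its late estimates describe PSA as if patients had stayed on study.
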